SYNOPSIS

PROTOCOL AnticipUSC – N°ICO 2016-A-04

A) Clinical Trial Identification

TITLE OF THE TRIAL: *Multicenter, open-label, randomized study comparing early postoperative prophylactic non-invasive ventilation in the intensive care unit versus standard postoperative follow-up in patients at high risk of postoperative pulmonary complications according to the preoperative ARISCAT score, undergoing surgery under general or regional anesthesia (ANTICIPUSC)*

SHORT TITLE: ANTICIPUSC

COORDINATOR: [name] [name]

ESTIMATED NUMBER OF CENTERS: 3

NUMBER OF PATIENTS: 266

B) Sponsor Identification

NAME OF THE ORGANIZATION: ICO, DRCI-Cellule de Promotion

CONTACT PERSON: MME [name]

[contact]

[contact]

C) General Information About the Trial

Indication:

This study will focus on a selected population at high risk of postoperative pulmonary complications (PPC) according to the ARISCAT score, among all surgical patients in the participating centers, whether undergoing surgery under General Anesthesia (GA) or Regional Anesthesia (RA), who may benefit from preventive postoperative management.

Primary objective:

The primary objective of the study is to compare the effectiveness of a preventive postoperative management strategy using non-invasive ventilation (NIV) in the intensive care unit versus standard care, on the incidence of acute respiratory failure within 7 postoperative days during hospitalization, in patients at high risk according to the ARISCAT score.

Secondary objectives:

- The safety and tolerability of the strategy under study
- The cause of acute respiratory failure (arf) among the different postoperative pulmonary complications (ppc)
- Mortality during hospitalization for surgery, up to a maximum of 7 days
- Any effect on patient reintubation (cause and timing)
- Any effect on the length of stay in the icu/intensive care unit and on invasive or non-invasive mechanical ventilation
- Any effect on the incidence of healthcare-associated infections, defined according to the centers for disease control (cdc) criteria.

Inclusion criteria:

1. Patient aged 18 years or older
2. Patient scheduled for elective surgery or considered semi-urgent (pre-anesthesia consultation < 48 hours before the surgical procedure), under General Anesthesia (GA) or Regional Anesthesia (RA)
3. Patient with an ARISCAT score greater than or equal to 45 (high risk of PPC)
4. Written informed consent signed by the patient

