
- Death from any cause during hospitalization for surgery

Assessment of an effect on patient reintubation:

- Reintubation due to respiratory failure (ARF)
- Reintubation due to non-respiratory failure, excluding reintubations specifically for a new surgical or interventional radiology procedure
- Time to reintubation to assess delayed reintubation (characterized by a non-significant difference in reintubation rate between groups but a longer delay in the NIV group)

Assessment of an effect on length of stay in ICU and duration of invasive or non-invasive mechanical ventilation:

- Number of days of invasive mechanical ventilation (intubated or tracheostomized) during hospitalization for surgery, including episodes of reintubation
- Number of days of non-invasive mechanical ventilation (NIV) during hospitalization for surgery, including prophylactic and therapeutic NIV.

**Assessment of an effect on the incidence of healthcare-associated infections, defined according to
Centers for Disease Control (CDC) criteria:**

- Infectious pneumonia: see secondary endpoint criteria
- Urinary tract infection: fever $> 38^{\circ}\text{C}$ and urine culture showing no more than two microbial species, at least one with a concentration $> 10^5 \text{ CFU/ml}$, in a patient with no other obvious source of infection
- Catheter-related infection: fever $> 38^{\circ}\text{C}$, positive catheter culture or sample, and resolution of fever within 48 hours after catheter removal without antibiotic change and no other identified source of infection
- Bacteremia: fever $> 38^{\circ}\text{C}$ and at least one positive blood culture (two or more if coagulase-negative staphylococcus)
- Surgical site infection

Data collection is performed prospectively throughout the first 7 days of hospitalization for surgery.

D) Description of Investigational Medicinal Products

MEDICAMENTS :

Name of the Medicinal Product (INN)	Brand Name	Pharmaceutical Form	Route of Administration	Dosage per Administration
Medical Liquid Oxygen	N/A	Gas	N/A	

Therapeutic regimen:

The ventilatory mode used will be an assisted mode (PSV or BiPAP), as these have shown a stronger (86) and more sustained effect (29) than CPAP alone.

The interface—nasal mask, face mask, or helmet—is chosen according to the unit's usual practice.

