Statistical analyses will be performed using R software and IBM SPSS.

A total of 266 patients are planned for inclusion, divided into two balanced groups.

DESCRIPTION OF PLANNED STATISTICAL METHODS:

Research Protocol

Patients will be analyzed on an intention-to-treat basis and then per-protocol.

Intention-to-treat analysis: all patients included in the study for whom outcome data are available will be considered in the analysis according to their randomization group. No imputation method will be used in case of missing data.

If organizational constraints prevent the patient from receiving prophylactic NIV (despite inclusion in the corresponding intervention arm), the patient will remain in their randomization arm for the entire study duration, and their data will be analyzed on an intention-to-treat basis.

Per-protocol analysis excludes patients for whom the initial protocol was not fully adhered to. Only patients who followed the protocol will be considered in the analyses, within the arm to which they were originally randomized.

The analysis will focus on the primary endpoint to determine whether randomization to the "PPC prevention strategy" arm leads to a reduction in PPC frequency compared to the control group. Effect size and number needed to treat will be calculated.

Similarly, for secondary endpoints, significant differences between the two groups will be sought in terms of:

- a) Safety and tolerability of the strategy under study (see safety assessment parameters)
- b) Mortality during hospitalization
- c) Patient reintubation
- d) Length of stay and duration of invasive or non-invasive mechanical ventilation

Description of the overall analysis method

The significance threshold is set at 0.05, and all tests will be two-sided. For qualitative variables, results will be reported as counts and percentages. For quantitative variables, results will be reported as means and standard deviations in case of normal distribution, and as medians with 25th and 75th percentiles in the absence of a Gaussian distribution. Normality of continuous variables will be assessed using the Kolmogorov-Smirnov test.

A simple descriptive analysis will be performed on the entire study population and by subgroups. This description will include sociodemographic data, medical history, ongoing treatments, etc.

A qualitative and quantitative analysis of missing data will be performed. No imputation of missing data is planned for the endpoints.

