Study of Associations (Qualitative and/or Quantitative Variables):

For each parameter of interest, a bivariate analysis will be performed, possibly complemented by a multivariate analysis adapted to the outcome variable to explore potential associations.

For bivariate analyses, the use of parametric or non-parametric tests will depend on sample size and/or variable distribution. The significance threshold is set at 0.05, and all tests will be two-sided.

The statistical test used will be Pearson's Chi-square test (or Fisher's exact test) for qualitative variables. For quantitative variables, the statistical tests used will be ANOVA or the non-parametric Kruskal-Wallis test.

The association between each presumed risk factor and the parameter of interest will be estimated using the relative risk (RR) and its 95% confidence interval.

A multivariate logistic regression analysis will estimate the adjusted RR and its 95% confidence interval for each retained factor (conservative threshold of 0.20 in univariate analysis).

Early Mortality:

Overall survival is defined as the time between the date of operating room discharge and the date of death if the patient dies within 7 days, or the end of study follow-up at Day 7. The Kaplan-Meier method will be used to estimate survival rates and plot survival curves. The Log-Rank test will be used to compare survival curves. Event-free survival is defined as the time between operating room discharge and the date of occurrence of the event (PPC) or the date of last follow-up if censored.

A semi-parametric Cox proportional hazards regression model will estimate for each variable the crude association (Hazard Ratio, HR) between the factor studied and death (bivariate analysis), then the adjusted HR in multivariate analysis.

The significance threshold for including other variables in the multivariate analysis will be 0.20. If several candidate variables are redundant, the most representative variable will be retained for the model.

Subgroup Analyses (Exploratory):

Subgroup analyses will address the occurrence of endpoints:

- According to patient characteristics at inclusion (medical history, ARISCAT score components, type of surgery, and planned anesthetic technique).
- The subgroup of patients receiving NIV as curative (under conditions noted at session start) will be compared to the group receiving NIV only prophylactically in terms of outcome at Day 7.

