- Identification of factors associated with failure of prophylactic NIV in the subgroup where NIV was prematurely discontinued.

Statistical Justification for Sample Size:

Previously described data indicate that the expected effect size is approximately a 50% reduction in events:

- In studies on medical populations, the effect of prophylactic NIV was observed even on harder endpoints than ours: -66% reduction in reintubation, -51% reduction in ARF incidence, and -50% reduction in reintubations, and again -69% reduction in ARF incidence.

- In surgical populations, prophylactic NIV has led to a reduction in restrictive syndrome of about 50%, an improvement in pulmonary function tests (PFTs) of +30%, and a decrease in length of stay by 7 days.
- In curative use after abdominal surgery—a more unfavorable situation since ARF is more advanced—Squadrone reported favorable outcomes in 90% of cases with CPAP, and reintubations were reduced by 30%.

Given that the expected incidence of ARF in the high-risk group is 30–50%, a sample size of at least 121 subjects per arm is required to demonstrate, under a two-sided hypothesis, a relative reduction of 50% in ARF between a group managed with prophylactic NIV (15%) and a group managed with standard care (30%), with an alpha risk of 5% and a beta power of 90%. We anticipate 10% of patients will be non-evaluable.

The required sample size is therefore $242 + 24 = 266$ high-risk subjects evaluated for PPC.

STATISTICAL STOPPING RULES:

No interim analysis is planned in the protocol. However, if during the review of safety and efficacy data provided to the independent monitoring committee (raw, descriptive, and summarized data without pre-established statistics by the investigator or sponsor), a highly significant difference is identified for the primary endpoint or one of the safety parameters when comparing the two groups blinded to treatment allocation, the committee may decide to stop the study.

METHOD FOR HANDLING MISSING, UNUSED, OR INVALID DATA:

Patients included in the study for whom an endpoint is not available will not be considered in the analysis for that missing endpoint. No imputation method will be used for missing data.

MANAGEMENT OF CHANGES TO THE INITIAL ANALYSIS PLAN:

Modifications to the initial analysis plan may be proposed by the monitoring committee (interim analysis, statistical tests, adverse events, secondary objectives) if new literature data justify them.

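### Ventilation-day endpoints cover the whole surgical stay but data stop at Day 7, and ICU length of stay has no definition or window, so neither yields a duration as planned

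*Combined protocol and SAP*

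**What the plan says.** **Ventilation.** Section C, Secondary endpoints, lists two day counts: "Number of days of invasive mechanical ventilation (intubated or tracheostomized) during hospitalization for surgery, including episodes of reintubation" and "Number of days of non-invasive mechanical ventilation (NIV) during hospitalization for surgery, including prophylactic and therapeutic NIV". Neither has a day limit.

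**Length of stay.** The objective is "Any effect on the length of stay in the icu/intensive care unit and on invasive or non-invasive mechanical ventilation". The endpoint heading is "Assessment of an effect on length of stay in ICU and duration of invasive or non-invasive mechanical ventilation", but the two bullets under it concern ventilation only. The list of comparisons in section E, item d, reads "Length of stay and duration of invasive or non-invasive mechanical ventilation", without saying ICU. No start, end or window for stay is given anywhere.

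**Window.** The secondary-endpoint list closes with "Data collection is performed prospectively throughout the first 7 days of hospitalization for surgery". The Early Mortality paragraph in section E refers to "or the end of study follow-up at Day 7", and section F gives a follow-up period of 7 days.

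**Analysis.** Quantitative variables go to ANOVA or Kruskal-Wallis (section E, Study of Associations). The missing-data rule leaves a patient out of the analysis of any endpoint that is unavailable, without imputation. No rule covers patients who are still ventilated, still in ICU or dead at Day 7.

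**The concern.** The ventilation endpoints as worded include days that will not be collected. What can be computed is a count limited to the observation window, while the heading and the list of comparisons call it a duration. ANOVA and Kruskal-Wallis would treat a cut-off value as a completed one.

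For invasive ventilation the error can have a direction. The reintubation endpoints in section C set out to detect later reintubation in the NIV arm without a lower rate. If that happened, the NIV arm would have fewer observable days after reintubation, and a possible harm on one endpoint could look like a benefit on another. Dropping unfinished episodes instead would remove the patients with the longest ventilation. Early death also gives a low day count, and no death rule prevents this from reading as a good result.

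For stay, differences that arise after Day 7 cannot be seen. The plan names shorter stay among its expected outcomes.

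**Working it through.** The plan gives no effect size, power or distribution for stay or ventilation days, so there is no figure of its own to reproduce. All distributions below are assumptions.

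**1. One ventilation episode.** Inputs: window of 7 days (section C), reintubation on day r, true length L. Counting the start day, recorded days = min(L, 8 − r).
- L = 10, r = 2: min(10, 6) = 6.
- L = 10, r = 5: min(10, 3) = 3. Three days are lost relative to r = 2, which is 3/6 = 50%, with the same true length.
- L = 2: 2 days for r = 2 and for r = 5. Episodes that end within the window are not affected.
- The most that can be recorded is 7, 6, 5, 4, 3, 2 or 1 days for r = 1 to 7, and 0 for reintubation after Day 7.
- If the start day is not counted, min(L, 7 − r) gives 5 and 2 for the 10-day episode. The gap is again 3 days, now 3/5 = 60%.

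**2. Average over reintubated patients.** Assume exponential lengths with mean m, the same in both arms, and reintubation after t elapsed days. The mean recorded value is m × (1 − exp(−(7 − t)/m)).

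| True mean m | t = 2 | t = 4 | Spurious difference |
|---|---|---|---|
| 5 days | 3.16 | 2.26 | 0.9 |
| 8 days | 3.72 | 2.50 | 1.2 |
| 12 days | 4.09 | 2.65 | 1.4 |

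**3. Whole arm.** Assume that 5, 10 or 15% of each arm are reintubated, all on Day 2 in one arm and all on Day 5 in the other, with long episodes and no other ventilation. The gap of 3 days per reintubated patient gives an arm-mean difference of 0.05 × 3 = 0.15, 0.10 × 3 = 0.30 or 0.15 × 3 = 0.45 day. In simulation with 121 per arm, the rank test (Mann-Whitney, equivalent to Kruskal-Wallis for two groups) rejects in about 5 to 8% of trials, against a nominal 5%.

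**4. Length of stay.** Assume log-normal stays rounded up to whole days, the NIV arm 20% shorter, 121 per arm, values cut at 7, and a Mann-Whitney test at 0.05 (20,000 simulations per row).

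| Control median (days) | Log-SD | Controls over 7 days | Mean difference, full → cut (days) | Power, full → cut |
|---|---|---|---|---|
| 3 | 0.5 | 5% | 0.68 → 0.61 | 0.91 → 0.91 |
| 3 | 0.7 | 11% | 0.77 → 0.55 | 0.66 → 0.66 |
| 5 | 0.5 | 25% | 1.14 → 0.68 | 0.92 → 0.90 |
| 5 | 0.7 | 32% | 1.28 → 0.55 | 0.67 → 0.63 |
| 7 | 0.5 | 50% | 1.59 → 0.53 | 0.92 → 0.86 |
| 7 | 0.7 | 50% | 1.79 → 0.46 | 0.67 → 0.58 |
| 14 | 0.5 | 92% | 3.17 → 0.11 | 0.92 → 0.43 |
| 14 | 0.7 | 84% | 3.57 → 0.18 | 0.67 → 0.37 |

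From unrounded values, the power loss is 0.00 to 0.03 at medians of 3 to 5 days and 0.06 to 0.48 at 7 to 14 days. Smaller runs of the same model gave 0.01 to 0.02 and 0.06 to 0.46, which agrees within simulation error. At a control median of 10 days the NIV median is 0.8 × 10 = 8; both exceed 7, so both recorded medians are 7.

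**The case against.** The strongest reply is that the endpoints are already capped. The mortality bullet uses the same in-hospital wording without a limit, yet the mortality objective is limited to 7 days, and the collection sentence closes the whole secondary list. On that reading, ventilation days within 7 days are a deliberate restricted endpoint. The reading is reasonable, but it does not settle the matter. The plan writes a cap for the primary endpoint and for mortality and none for stay or ventilation. Even a capped count is not a duration, and it still needs rules for ongoing episodes and deaths.

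The reply is also right that delay is not hidden, because time to reintubation is a separate endpoint. It is right too that ICU stays may be short, in which case the cut costs almost no power.

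A reader might infer stronger claims that the documents do not support:
- *Stay is defined over the whole hospitalization.* It is not defined at all, and the objective and endpoint heading name only ICU stay.
- *Every long stay will be recorded as 7 days.* This is likely but not written; the missing-data rule could lead to exclusion instead.
- *Later reintubation always scores as shorter ventilation.* This holds only for episodes that outlast the window.
- *The NIV arm would show 50 or 60% fewer ventilation days.* Those figures are for one long episode, not an arm mean.
- *The trial aims to show the cited "a decrease in length of stay by 7 days".* That phrase is background to the sample size for acute respiratory failure. It is not a target for stay and does not say which stay is meant.

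**Conclusion.** The concern holds for secondary endpoints. The two ventilation-day endpoints cannot be computed as defined from data that stop at Day 7, and ICU stay has neither a definition nor a window. This is more than missing detail: the planned tests would run on cut-off values, and the cut can favour the arm with later reintubation.

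The size is conditional. Per long episode, a shift in reintubation from Day 2 to Day 5 removes 3 recorded days. At arm level this is 0.15 to 0.45 day if 5 to 15% are reintubated, and the rank test seldom turns it into a significant result. For stay, the recorded mean difference shrinks in every scenario examined, but a material power loss needs a typical stay of about 7 days or more, and the documents give no figure for that. The primary endpoint is explicitly a 7-day endpoint and is not affected. The sponsor should correct this, and the correction is cheap.

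**What to change.** Choose one of two routes and align section C with section E.

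**Route 1, full duration.** At the end of the surgical stay, take from the existing record the dates of ICU discharge, of hospital discharge or death, and of the start and stop of each ventilation episode. Define stay, and derive the endpoints from these dates. Cost: a few dates per patient and no extra visit or procedure; the case report forms of long-stay patients close later.

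**Route 2, 7-day quantities.** This changes only wording and analysis rules.
- Restate both ventilation endpoints as days within the first 7 postoperative days.
- Define stay as ICU stay with a stated start, and analyse it as time to ICU discharge, censored at Day 7, with death as a competing event.
- Use ventilator-free days to Day 7 with death scored as zero, or an equivalent death rule.
- State that ventilation days to Day 7 are not a duration effect and must be read together with time to reintubation.

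Under either route, state that an episode or stay ongoing at Day 7 is not to be handled as a missing endpoint.

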NIV sessions of 1 hour are repeated every 2 to 3 hours, aiming for a daily assistance duration of 6 to 8 hours for a minimum of 24 hours. Weaning from NIV is managed by the clinician within a maximum of 48 hours.

Initially set between +5 and +8 cmH₂O, IPAP is gradually increased in increments of 2 to 3 cmH₂O for patient comfort, until achieving an inspiratory peak allowing an expired tidal volume (Vte) between 6–8 ml/kg of predicted body weight, according to current ventilation recommendations (84, 112), with a respiratory rate $< 30/\text{min}$.

PEEP is set between +5 and +10 cmH₂O, and FiO₂ adjusted to maintain SpO₂ $> 92\%$ or PaO₂ $> 70 \text{ mmHg}$ on blood gas analysis. Care is taken to ensure that total pressure (PEEP + IPAP) remains $\leq 20 \text{ cmH}_2\text{O}$ to avoid gastric distension (airway pressure lower than the lower esophageal sphincter pressure) (42) and to minimize the theoretical risk of bronchial suture dehiscence in thoracic surgery.

The ventilator's inspiratory trigger is set to the minimum value allowing the most sensitive detection of inspiratory efforts without causing auto-triggering.

The clinician may adjust IPAP based on the patient's blood gas results.

Duration of Treatment:

Each prophylactic NIV session lasts 1 hour. Sessions are repeated every 2 to 3 hours, separated by 2-hour periods without assisted ventilation to allow the patient to rest, eat, and receive care, including physiotherapy sessions. This schedule may be adapted to the unit's activity, with the goal of achieving a daily assistance duration of 6 hours without exceeding 8 hours, for a minimum of 24 hours.

Weaning from NIV is managed by the clinician within a maximum of 48 hours.

Expected outcomes:

Prevent the occurrence of PPCs and the complications they cause:

- Infectious pneumonia and aspiration pneumonia
- Pleural effusions
- Atelectasis
- Bronchospasm
- Acute respiratory failure (ARF) and hypoxemia, and consequently:
 - Prevent patient reintubation
 - Prevent surgical site infections and anastomotic suture dehiscence
 - Reduce morbidity and mortality related to reintubation, and shorten length of stay
 - Avoid the need for invasive mechanical ventilation and all associated complications:
 - Nosocomial infections, including ventilator-associated pneumonia (VAP) due to micro-aspirations linked to the endotracheal tube
 - Delayed rehabilitation
 - Communication difficulties
 - Discomfort

E) CONSIDERATIONS STATISTIQUES

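### Total NIV days is tested as an effect of the strategy, although the between-arm difference is largely built in by allocation

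*Combined protocol and SAP*

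**What the plan says.** All references are to the combined protocol and SAP.

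- **Secondary endpoints (part C).** Under "Assessment of an effect on length of stay in ICU and duration of invasive or non-invasive mechanical ventilation" the plan lists "Number of days of non-invasive mechanical ventilation (NIV) during hospitalization for surgery, including prophylactic and therapeutic NIV". Days of invasive ventilation are a separate item. The secondary objectives likewise speak of an effect on ventilation.
- **Planned statistical methods (part E).** The plan states that "for secondary endpoints, significant differences between the two groups will be sought in terms of" four items, of which item d is "Length of stay and duration of invasive or non-invasive mechanical ventilation". It adds: "The significance threshold is set at 0.05, and all tests will be two-sided".
- **Study of Associations (part E).** "For quantitative variables, the statistical tests used will be ANOVA or the non-parametric Kruskal-Wallis test".
- **Therapeutic regimen (part D).** The intervention arm has repeated NIV sessions, "aiming for a daily assistance duration of 6 to 8 hours for a minimum of 24 hours", with weaning inside 48 hours.
- **Subgroup Analyses (part E).** The only analysis that separates the two uses of NIV is exploratory: "The subgroup of patients receiving NIV as curative (under conditions noted at session start") is set against patients who had prophylactic NIV only. That comparison is not between randomised arms.

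Total NIV days, prophylactic sessions included, is therefore an endpoint tested between arms and labelled as an effect.

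**The concern.** An effect endpoint should respond to what the treatment does to patients. This one also counts the treatment. A patient in the NIV arm who receives the assigned regimen has about one to two NIV days before any complication can occur, while a control patient starts from none. Any saving in therapeutic NIV has to be seen through that offset.

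The test can therefore give the same answer, more NIV days in the NIV arm, whether prophylaxis prevents ARF or does nothing. Reported as an effect on ventilation duration, that answer could be taken to mean that the strategy prolongs ventilatory support. The informative question, whether prophylaxis spares patients therapeutic NIV, has no randomised comparison in the plan.

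**Working it through.** **Plan's own figure.** The plan gives none for NIV days. The sample-size section gives 121 per arm, used here only as the group size. (For ARF 30% v 15%, 121 per arm gives 80.2% power; the stated 90% would need 161. That is a separate matter and does not affect this point.)

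**Inputs from the documents.** 121 evaluable per arm; two-sided 0.05; Kruskal-Wallis or ANOVA; ARF 30% in controls and 15% with NIV as the target, with 30–50% as the expected range; prophylaxis for 24 to 48 h; data collected for 7 days; organisational non-delivery foreseen, with the patient kept in the NIV arm and no rate given.

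**Assumptions not in the documents.** Delivered prophylaxis adds 1 or 2 days (mean 1.5). Therapeutic NIV lasts 1 to 4 days (mean 2.5) and is given to a share *q* of ARF patients, with *q* = 1 or 0.5. Controls receive no prophylactic NIV. Delivery *d* in the NIV arm ranges from 10% to 100%.

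**Step 1: expected difference in total NIV days (NIV arm minus control).**

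Δ = 1.5 × *d* − 2.5 × *q* × (ARF control − ARF NIV)

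- No effect on ARF: Δ = 1.5 × *d*, so +1.50 days at full delivery, +1.05 at 70%, +0.75 at 50% and +0.45 at 30%.
- ARF halved, 30% to 15%, *d* = 0.9: with *q* = 1, 1.35 − 2.5 × 0.15 = +0.98; with *q* = 0.5, 1.35 − 0.19 = +1.16. The therapeutic saving (0.38 or 0.19 day) is real, but the total still rises.
- Delivery at which the sign turns, for 30% to 15%: 0.375 / 1.5 = 25% (*q* = 1) or 0.1875 / 1.5 = 12.5% (*q* = 0.5). For 50% to 25%: 0.625 / 1.5 = 42%, or 0.3125 / 1.5 = 21%.

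**Step 2: how often the planned test is significant** (simulation, 1,500 trials per scenario, Kruskal-Wallis on total NIV days; ranges span *q* = 1 and 0.5).

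| ARF, control / NIV | Delivery | Significant |
|---|---|---|
| 30% / 30% | 70–100% | 100% |
| 30% / 30% | 50% | 99.7–100% |
| 30% / 30% | 30% | 84–98% |
| 30% / 30% | 10% | 17–37% |
| 50% / 50% | 70–100% | 99.9–100% |
| 50% / 50% | 50% | 96–99.9% |
| 50% / 50% | 30% | 61–90% |
| 30% / 15% | 70–100% | about 100%, NIV arm higher |
| 50% / 25% | 90% | 99–100%, NIV arm higher |
| 50% / 25% | 70% | 78–100%, NIV arm higher |

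In the no-effect rows at 30% delivery or more, significance was always towards more NIV days in the NIV arm. With exactly one prophylactic day, *q* = 1 and ARF 30% in both arms, the figures are 100% at 90% delivery, 98.9% at 50% and 75% at 30%. ANOVA at ARF 30% in both arms gives 100% at 70% delivery or more and 98–99.8% at 50%.

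**Step 3: the same data, therapeutic NIV days only.** With no effect on ARF (30% in both arms), Kruskal-Wallis rejects in 4–7% of trials, close to nominal. With 30% v 15%, power is about 80% (*q* = 1) or 46% (*q* = 0.5). With 50% v 25% it is about 98% or 71%.

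**Step 4: a weakness of the alternative.** Suppose ARF is 30% in both arms, but half of the ARF patients in the NIV arm are intubated directly. Therapeutic NIV is then used in 30% × 0.5 = 15% v 30%, the same pattern as the benefit scenario, and about 82% of trials show a reduction that reflects no benefit.

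**The case against.** The strongest reply is that nothing here is an error. The definition says openly that prophylactic NIV is counted, total NIV use really is higher in an arm assigned to NIV, and net NIV burden is a fair outcome for a strategy trial. Efficacy is judged on blinded-adjudicated ARF and on reintubation, and invasive ventilation days are kept apart. All of this stands. It makes the point one of interpretation, confined to a secondary endpoint.

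A reader might infer more than the documents support, in three ways:

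- **That the 96–100% is an inflated type I error.** It is not. Equal ARF is not the null hypothesis for total NIV days, and the test correctly finds a true difference in exposure.
- **That significance is certain and every therapeutic saving is hidden.** Both depend on delivery. At 10–30% delivery with no effect on ARF, the rate runs from 12% to 98% across the 30% and 50% scenarios, and with low delivery and a large effect the total can fall. The plan foresees non-delivery without giving a rate. In the per-protocol analysis, however, delivery is high by construction, so the built-in difference is at its fullest.
- **That therapeutic NIV days would be a clean replacement.** Direct intubation or death lowers that count (step 4), and its power depends on how many ARF patients receive NIV, which the plan does not state.

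The absence of prophylactic NIV in controls is also an inference. The document does not define standard care, although it says that NIV-arm patients who cannot be given prophylaxis are followed as controls are.

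What the reply does not answer is the label and the test. The quantity is listed as an effect and tested as one, and no randomised comparison looks at therapeutic NIV alone.

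**Conclusion.** The point holds in a limited form. The between-arm test of total NIV days mainly detects the allocation. Under the stated assumptions it shows significantly more NIV days in the NIV arm in about 96–100% of trials when ARF is equal in both arms (30% or 50%) and at least half of that arm receives prophylaxis. With ARF 30% and 30% delivery the figure is roughly 75–98%. It remains about 100% when ARF is truly halved from 30% to 15% and at least 70% receive prophylaxis. A result that is the same with and without benefit cannot show whether the strategy works.

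The figures rest on assumed durations of prophylactic and therapeutic NIV, on no prophylactic NIV in controls, and on an unknown delivery rate. The primary endpoint and its analysis are not affected. The change is worth making because the built-in difference is close to certain at reasonable delivery and the correction is cheap.

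**What to change.** - **Endpoint (part C) and item d (part E).** Make the NIV endpoint tested between arms the number of days of therapeutic (curative) NIV in the first 7 postoperative days. Classify each session's purpose when it starts, by one written rule applied identically in both arms. Do not tie the count to an adjudicated ARF onset date: the committee is said to validate that ARF occurred, not to date it.
- **Prophylactic and total NIV days.** Report both by arm descriptively, as exposure, adherence and burden, without a test of effect.
- **Interpretation.** State in advance that therapeutic NIV days will be read together with invasive ventilation days, reintubation and death, so that fewer NIV days caused by direct intubation or death are not taken as benefit.

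**Cost.** This rewords one secondary endpoint and one analysis line; the sample size and primary analysis stay as they are. The subgroup section suggests that purpose is already noted at session start, but does not show that it is recorded in the same way for controls, so the case report form should be checked. Two downsides remain: classification is made open-label, and power is uncertain (about 80% if every ARF patient receives NIV, about 46% if half do, at 30% v 15%).
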